Statistical Analysis	
The rates of all adverse events occurring within 24 hours post procedure, hospital discharge status and after discharge for all opened devices at each participating clinical site during the surveillance period will be summarized. The numbers of individual adverse events of each type and the per subject incidence rate for each type of adverse event will be determined and reported along with 90% two-sided exact binomial confidence intervals. Separate event counts and incidence rates with corresponding confidence intervals will be summarized for adverse events determined to be serious, device-related, serious and device-related, procedure-related, serious and procedure-related, and severe. Listings for all adverse events will be compiled that provide full descriptions of each adverse event including determination of the severity, seriousness, and relationship to the device or procedure. Discharge status will be described with counts and percentages.
 
Effectiveness at six months will be descriptively summarized in terms of the number and percentage of subjects achieving successful aneurysm occlusion measured by Raymond scale grade I and II and by clinical outcome as measured by mRS shift analysis comparing preprocedure mRS (up to 24 h prior to treatment) with 6 month mRS. In addition, tetrachotomized (0,1, 2, 3-6) mRS analysis will also be performed. mRS will also be evaluated at discharge and 30 days. Successful aneurysm occlusion will also be evaluated at the end of procedure. Stability of occlusion will be evaluated by comparing the two angiographic studies that are 6 months apart. The distribution of scores will be summarized by counts and percentages. If only three month Raymond scale value is available but not the six month, the three month value will be used in these analyses. Similarly, the last available earlier mRS values will be used if the six month value is not available.

-----------------------------	--

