### **Efficacy**

- Successful intracranial aneurysm occlusion (measured by Raymond Roy classification I or II) at the end of procedure, using digital subtraction angiography (DSA).
- Successful intracranial aneurysm (IA) occlusion, that is a stable IA occlusion, measured by Raymond Roy classification I or II taken at 6 months ( $\pm 21$ d) post procedure without the need for re-treatment of the target IA, using DSA.
- Good clinical outcome- mRS shift @ 6 months (change @ 6 months from pre procedure) and tetrachotomized (0,1, 2, 3-6) mRS analysis.

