## **5.2 Site Selection, Training and Initiation**

### **5.2.1 Selection**

Sites will be selected by their ability to provide complete data sets with robust analyses for all safety and effectiveness outcomes with minimal risk to the subjects (i.e. CT up to 24h post procedure and 6 months angio to determine Raymond Scale score).

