#### **7.7 180 days ( $\pm$ 21 days)**

- mRS Score (If an in-person visit cannot be performed, it is possible to perform via structured telephone interviews)-should be assessed by an independent clinician who is not a member of the investigational team.
- Raymonds scale, using DSA
- Complications and any AE's (including a determination of the severity, seriousness, and relationship to the device or procedure). These will specifically include stroke, hemorrhage and death.
- Antiplatelet and/or anti-coagulant Medications, if was changed from previous visit

In some cases, this visit is also performed at 3 months ( $90 \pm 14$  days) as a standard of care, then the same information will be collected at 3 months as well.

Also note, if in-person visits are not possible, mRS assessments may be performed remotely by structured telephone interviews.

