**Table 2: Schedule of Events**

Elapsed time/Study procedures	Baseline/Procedure	24 hours (-6/+12)	Discharge if different than 24 hours (-6/+12)	30 ( $\pm 7$ ) days	180 ( $\pm 21$ ) days**
Informed Consent	X				
Demographics	X				
Medical History and Concomitant Medications	X				
Brain CT Scan	X	X *			
Vital Signs	X				
mRS score +	X		X	X	X
NIHSS	X			X	
Clinical Laboratory	X				
Raymond scale	X***				X***
Intraoperative data	X				
Prior/concomitant medications	X	X	X	X	X
Adverse Events	X	X	X	X	X

(\*) If performed as a standard of care any time up to 24 hours post procedure

(\*\*) Will be collected if performed also at 90 ( $\pm 14$ ) days as a standard of care.

(\*\*\*) Post-procedure and 6 months imaging should use Digital Subtraction Angiography (DSA) for Raymond scale assessments.

(+) If in-person visits are not possible, mRS assessments may be performed remotely by structured telephone interviews.

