### **8.4 Six Month Effectiveness and Clinical Status**

Effectiveness at six months will be descriptively summarized in terms of the number and percentage of subjects achieving stable IA occlusion, measured by Raymond Roy classification I or II without the need for re-treatment of the target IA and good clinical outcome defined by mRS and shift tetrachotomized (0,1, 2, 3-6) analysis. 95% two-sided confidence intervals will be provided to evaluate the statistical precision of the estimates. If these endpoints are available at three months but not at six months, the three month values will be used for these analyses.

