### **8.6 Missing Data**

Since the primary safety endpoint is defined immediately post-procedure and up to 30 days, the amount of missing data for this study is anticipated to be low and so no imputation of missing data will be performed. For the analysis of six month effectiveness, if the six month Raymond score or mRS values are missing and any earlier data are available, the most recent earlier value will be used.

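### Section 8.6, read literally, lets the end-of-procedure Raymond grade stand in for a missing six-month grade, against the endpoint definition, the Protocol Summary and Section 8.4

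*Combined protocol and SAP*

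**What the plan says.** Three places in the combined protocol and SAP say what to do when a six-month value is missing.

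- Section 8.6 covers Raymond and mRS together: "if the six month Raymond score or mRS values are missing and any earlier data are available, the most recent earlier value will be used". The preceding statement that nothing will be imputed is tied to the primary safety endpoint.
- Section 8.4 also covers both outcomes: "If these endpoints are available at three months but not at six months, the three month values will be used for these analyses".
- The Protocol Summary (Statistical Analysis) separates them. For Raymond: "If only three month Raymond scale value is available but not the six month, the three month value will be used in these analyses". For mRS: "the last available earlier mRS values will be used if the six month value is not available".

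Section 3.1 (Efficacy) defines the endpoint as stable occlusion without re-treatment, "measured by Raymond Roy classification I or II taken at 6 months". The Protocol Summary adds that stability is judged by comparing two angiograms six months apart.

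Table 2 schedules a Raymond grade twice, at the procedure and at 180 days. On the three-month visit, Section 7.7 says "In some cases, this visit is also performed at 3 months", and the note to Table 2 says "Will be collected if performed also at 90".

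**The concern.** Section 8.6 sets no limit on how early the substitute may be. For a subject with no follow-up angiogram, the only earlier Raymond grade is ordinarily the one read at the end of the procedure. Carrying it forward compares a single angiogram with itself, so the subject is stable by construction. The rule makes no exception for a subject who died or was lost.

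Two analysts, one following Section 8.4 and the other Section 8.6, would report different numerators and denominators for the same listed efficacy endpoint, and nothing in the text says which section governs. If occlusion is less frequent at six months than at the end of the procedure, the reported rate moves toward the procedural rate. The 95% interval that Section 8.4 offers as a measure of precision would also count subjects with no six-month observation in its denominator.

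**Working it through.** **1. The texts side by side, for a subject with no six-month Raymond grade**

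| Situation | Protocol Summary | Section 8.4 | Section 8.6 |
|---|---|---|---|
| Three-month grade exists | use it | use it | use it |
| Only the end-of-procedure grade exists | no substitute named | no substitute named | use end-of-procedure grade |

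The rules part only in the second row. For mRS, the Protocol Summary and Section 8.6 agree on the last earlier value, while Section 8.4 names three months only.

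**2. The plan's own figure.** Section 8.1 gives 90 evaluable patients for end-of-procedure occlusion (performance goal 69.7%, assumed rate 82.6%, one-sided 0.025, power 80%).

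n = [(1.960·√(0.697·0.303) + 0.842·√(0.826·0.174)) / (0.826 − 0.697)]² = 89.4, rounded up to 90.

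It reproduces. It concerns the end-of-procedure endpoint, so the six-month rule does not touch it.

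**3. Size of the effect (illustration).** The documents give neither the share of subjects without a follow-up DSA nor the true six-month rate. Inputs:

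- N = 90 and end-of-procedure success 0.826 (Section 8.1);
- k carried forward = 9 or 27 (10% or 30% of 90; assumed);
- true six-month success s, equal in imaged and unimaged subjects (assumed).

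Reported rate = [(90 − k)·s + k·0.826] / 90, so bias = (k/90)·(0.826 − s).

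Coverage is the probability that an exact (Clopper-Pearson) 95% interval on n = 90 contains s, with successes distributed as Binomial(90 − k, s) + Binomial(k, 0.826). Section 8.4 names no interval method; exact is assumed, as Section 8.2 uses for adverse events.

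| s | k = 9: reported (bias), coverage | k = 27: reported (bias), coverage |
|---|---|---|
| 65% | 66.8% (+1.8), 94.5% | 70.3% (+5.3), 83.9% |
| 70% | 71.3% (+1.3), 95.3% | 73.8% (+3.8), 89.2% |
| 75% | 75.8% (+0.8), 95.8% | 77.3% (+2.3), 93.4% |
| 80% | 80.3% (+0.3), 96.5% | 80.8% (+0.8), 96.2% |
| 85% | 84.8% (−0.2) | 84.3% (−0.7) |

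At s = 82.6% the bias is zero. With observed grades only, coverage for s from 65% to 75% is 96.1% to 97.2%.

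Expected successes with no follow-up image: 9 × 0.826 = 7.4 and 27 × 0.826 = 22.3.

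**4. Interval width at about s = 70% (exact 95%)**

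| | Carried forward | Observed only |
|---|---|---|
| k = 9 | 64/90: 60.6%–80.2% (19.6 points) | 57/81: 59.2%–80.0% (20.8 points) |
| k = 27 | 66/90: 63.0%–82.1% (19.1 points) | 44/63: 57.0%–80.8% (23.8 points) |

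**The case against.** The best defence is that the texts need not be read as opposed. The Protocol Summary and Section 8.4 say what to do when a three-month value exists; they do not forbid another substitute when it does not. That is fair, and where a three-month grade is available all three agree. But if the rules are read as a hierarchy, with three months first and anything earlier next, the end-of-procedure grade is still used. The clash with a grade taken at six months remains on either reading.

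Second, the stability comparison in the Protocol Summary requires two angiograms, which might be taken to block a procedural grade. It does show that the literal result was probably not intended. Section 8.6 nevertheless names the Raymond score and admits any earlier data, and no text gives the other provisions precedence. A three-month substitute also strains the six-months-apart wording, so that sentence cannot settle the matter alone.

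Third, the practical effect may be small. Sites are chosen partly for their ability to provide "6 months angio to determine Raymond Scale score", which favours the low end of the assumed missing range, although Section 7 leaves procedures, including the six-month follow-up, to local practice. The endpoint is descriptive, with no test or performance goal. This objection stands and limits the weight of the point.

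**Conclusion.** The mismatch is established from the text and needs no assumption: Section 8.6 as written admits an end-of-procedure grade as a six-month result, contrary to Section 3.1 and to the stability comparison, and more broadly than the Protocol Summary or Section 8.4 provides.

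The size is conditional. Upward bias requires true six-month success below the end-of-procedure rate. With 9 of 90 carried forward and a true rate of 65% to 75%, the bias is 0.8 to 1.8 points and coverage stays at 94.5% to 95.8%. With 27 it is 2.3 to 5.3 points and coverage is 83.9% to 93.4%. At 80% the bias is under 1 point and coverage is not impaired.

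A reader might infer that the six-month rate will be materially inflated, or that its interval will be too narrow to trust. The documents do not support that. They give no six-month rate and no missing share, and material under-coverage needs both many carried grades and a true rate well below 82.6%. Nor does the point reach the primary effectiveness test, N=90 or 30-day safety. The rule should be corrected, but for a descriptive endpoint only.

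**What to change.** In Section 8.6, replace the last sentence with:

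> If the six-month Raymond grade is missing, the three-month grade, or otherwise the most recent post-discharge follow-up DSA grade, will be used; the end-of-procedure grade will not be carried forward. If the six-month mRS is missing, the most recent earlier value will be used.

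This keeps genuine follow-up images from unscheduled visits (Section 7.8), which a strict 90 (±14) day limit would discard. Align the last sentence of Section 8.4 and the Protocol Summary with it for both Raymond and mRS; otherwise Section 8.4 would still name only three months for mRS. Report the numbers of observed and substituted six-month Raymond grades beside the rate.

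The cost is a few sentences and two counts. Section 8.1 records FDA approval of the change in the number of deployments, so this edit may need the same step. The statistical price is that fewer subjects contribute a grade and the interval widens, as the observed-only column for 81 and 63 subjects shows. The rate among graded subjects can still be biased if those without a DSA do worse; the counts show how far that could matter but do not remove it.

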## **7.3 Procedure**

### **7.3.1 Angiography**

Intraprocedural diagnostic catheter angiography will be conducted prior to device deployment to determine location and aneurysm morphological features. Diagnostic angiograms will be obtained as per standard of care. A final post-procedure angiogram (full A-P lateral image) will be obtained once all treatments have concluded, including rescue therapy, if necessary. CT of up to 24h postprocedure if performed as a standard of care will be analyzed for safety parameters, such as hemorrhage.

Angiography at end of procedure and 6 months, will be analyzed to determine Raymonds scale at both time points and stability of Raymond Roy score. All images are to be de-identified and submitted to the core lab for review:

The University of California at Los Angeles with the following address:

Angiography and Noninvasive Imaging Core Lab  
[name], FAAN, FAHA, FANA  
UCLA Department of Neurology  
Neuroscience Research Building  
[name]  
[name]

Procedure will be handled as standard of care, according to Comaneci device IFU, appendix A.

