### 7.4 24 Hour (-6/+12) Follow-up

24 hours (-6/+12 hours) from time of procedure

- Complications and any AE's (including a determination of the severity, seriousness, and relationship to the device or procedure). These will specifically include stroke, hemorrhage and death.
- Concomitant antiplatelet and/or anticoagulant medications
- mRS Score (if performed) mRS should be assessed by an independent clinician who is not a member of the investigational team.
- CT (if performed up to 24 hours post procedure as a standard of care)
- If subject discharged within 24 h- Discharge status (for example, by CMS Patient Discharge Status Code)

**Note:** CT images will be sent to the Imaging Core Lab for evaluation.

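### Section 8.6 lets an end-of-procedure Raymond grade stand in for the six-month grade, so a subject with no follow-up angiogram can be counted as a six-month stable occlusion

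*Combined protocol and SAP*

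**What the plan says.** Section 3.1 (Efficacy) lists as an endpoint "Successful intracranial aneurysm (IA) occlusion, that is a stable IA occlusion, measured by Raymond Roy classification I or II taken at 6 months", by DSA and without re-treatment of the target aneurysm. The synopsis (Statistical Analysis) adds: "Stability of occlusion will be evaluated by comparing the two angiographic studies that are 6 months apart". Section 7.3.1 likewise says that end-of-procedure and six-month angiography "will be analyzed to determine Raymonds scale at both time points and stability of Raymond Roy score".

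Table 2 schedules Raymond grading at baseline/procedure and at 180 days only. Under section 7.7, three-month data are collected only where that visit is standard of care. Section 7.8 allows unscheduled assessments when clinically indicated.

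Three places deal with a missing six-month value:

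- **Section 8.6**, for Raymond and mRS alike: where six-month "values are missing and any earlier data are available, the most recent earlier value will be used".
- **Section 8.4**, for both endpoints: "If these endpoints are available at three months but not at six months, the three month values will be used for these analyses".
- **Synopsis**, for Raymond: "If only three month Raymond scale value is available but not the six month, the three month value will be used in these analyses". For mRS: "Similarly, the last available earlier mRS values will be used if the six month value is not available".

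Section 8.4 reports the six-month results descriptively, with 95% two-sided intervals.

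**The concern.** The endpoint is meant to show that occlusion lasted. A grade recorded at the end of the procedure says nothing about durability, yet section 8.6 lets it fill the six-month cell. A subject who left with grade I or II, was never imaged again and has no known re-treatment becomes a six-month success. Section 8.6 makes no exception for death or loss to follow-up.

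Missing six-month DSA is foreseeable. Follow-up is according to each site's standard practice (section 7). The 180-day mRS can be taken by telephone, but a DSA cannot (section 7.7). Surveillance runs until 30-day status is complete for 90 deployments (section 6), so six-month completeness is not a condition for stopping. The low missingness that section 8.6 expects is argued from the 30-day safety endpoint.

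At stake are the meaning and the apparent precision of a listed efficacy endpoint. The reported rate would mix day-0 with follow-up results, and a reader could not tell how many successes had no follow-up image.

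**Working it through.** **The plan's own figure.** The documents give no figure for the six-month endpoint or for missing six-month DSA. The sample size in section 8.1 concerns end-of-procedure occlusion: n = [(1.96·√(0.697·0.303) + 0.842·√(0.826·0.174)) / 0.129]² = 89.4, rounded up to 90. It reproduces, and the carry-forward rule plays no part in it.

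**Which value is carried.**

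| Angiograms available | Six-month value under 8.6 |
|---|---|
| 180-day DSA | the 180-day grade |
| no 180-day DSA, but a 3-month, unscheduled or between-window DSA | the latest of these |
| none after the procedure | the end-of-procedure grade |

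Only the last row is at fault. If section 8.4 and the synopsis are read as the rule and section 8.6 as the fallback, the fallback in that row is still the day-0 grade.

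**Size: inputs.** From section 8.1: 90 subjects and 82.6% grade I/II at end of procedure, hence 17.4% not I/II (treated as grade III). Everything else is assumed: *m*, the share with no post-procedure angiogram; *L*, the share of I/II lost by six months; *i*, the share of grade III that improves; *k*, the share of losses known through re-treatment. Missingness is taken as unrelated to outcome.

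**Formulas.**
- True rate = 0.826(1−L) + 0.174i
- Rate from carried grades = 0.826(1−Lk)
- Reported rate = (1−m)·true + m·carried
- Bias = m[0.826·L(1−k) − 0.174·i]

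**Worked case: L = 15%, i = 0, k = 0.** True rate = 0.826 × 0.85 = 70.2%. Half-width = 1.96·√(p(1−p)/n).

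| m | Reported | Bias | Half-width, carried grades counted (n = 90) | Half-width, imaged subjects only |
|---|---|---|---|---|
| 10% | 71.4% | +1.2 | 9.3 | 10.0 (n = 81) |
| 30% | 73.9% | +3.7 | 9.1 | 11.3 (n = 63) |

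For a given loss rate this case gives the largest upward bias, because no loss is known and no grade III improves. At 30% missing, the 3.7 points fall to 2.2 with i = 30%, to 1.9 with k = 50%, and to 0.3 with both.

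**Range over L 5-25%, i 0-30%, k 0-50%.**
- m = 10%: minimum 0.1(0.826·0.05·0.5 − 0.174·0.3) = −0.3 points; maximum 0.1·0.826·0.25 = +2.1.
- m = 30%: the same expressions times three, −1.0 (−0.95) to +6.2.

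Across 180 combinations over these ranges, with m from 10% to 30%, the bias was upward in 162 and the carried-forward interval was narrower than the observed-data interval in all 180.

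**Direction.** With k = 0 the bias is upward while i < 0.826L/0.174, that is below 24%, 47% or 71% for L = 5%, 10% or 15%.

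**Bounds in the worked case.** Missing as failure: 0.9 × 70.2 = 63.2% and 0.7 × 70.2 = 49.1%. Missing as success: 63.2 + 10 = 73.2% and 49.1 + 30 = 79.1%.

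**The case against.** The strongest points on the other side are these.

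- **Later angiograms exist.** A reader might infer that every subject without a three- or six-month DSA receives the day-0 grade. That goes too far. An unscheduled DSA, or one between the visit windows, is more recent and would be used. The fault is confined to subjects with no post-procedure angiogram.
- **Self-comparison is not stated.** It is tempting to say that the plan compares one angiogram with itself. The tabulated endpoint is grade I/II without re-treatment, and the two-angiogram comparison is a separate sentence in the synopsis. Nothing says that a substituted grade enters that comparison. What stands is that such a subject counts as a stable occlusion without a second image.
- **The sections can be reconciled.** The synopsis links its Raymond and mRS rules, and section 8.4 plus section 8.6 can be a rule with a fallback. The texts therefore do not prove a contradiction, or that section 8.6 is broader than intended. The fallback still gives the result described.
- **mRS.** Read literally, any earlier score includes the pre-procedure one, which would make the shift zero. A reader might infer that this would be common. It should be rare: surveillance continues until 90 deployments have complete 30-day status, which includes mRS (sections 6, 8.1 and 8.3). This is a wording point only.
- **Size.** Every rate is assumed. Selecting sites for six-month angiography (section 5.2.1) should keep missingness down, and at 10% missing the bias is small beside a half-width of 9 to 10 points. This stands and limits the weight of the point.

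**Conclusion.** The point holds in this limited form. As written, section 8.6 counts a day-0 grade I/II as six-month stable occlusion when there is no post-procedure angiogram and no known re-treatment. That does not fit the endpoint in section 3.1 or the way the synopsis judges stability.

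Under the assumed rates the effect is about -0.3 to +2.1 points at 10% missing and -1.0 to +6.2 at 30% missing. The documents do not support a claim that the rate is always inflated: if enough grade III aneurysms improve, the bias is downward. False precision is the steadier effect, since the interval was too narrow in every combination computed. These figures rest on the 82.6% planning rate, on missingness unrelated to outcome, and on missing, loss and improvement rates that the documents do not give.

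Nor do the documents support a reading in which the primary result is at risk. The six-month endpoint is descriptive (sections 8.1 and 8.4), and the performance-goal test and N=90 are untouched. The point should be fixed, but it does not threaten the trial's main conclusion.

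**What to change.** Put one rule in the synopsis, section 8.4 and section 8.6:

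- The end-of-procedure grade may not substitute for a missing six-month Raymond grade.
- The most recent post-procedure DSA may, whether three-month, unscheduled or between windows. A three-month-only rule would discard later images, including clinically prompted ones that show recurrence.
- Known re-treatment counts as failure, as sections 3.1 and 8.4 already define.

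Report the rate among subjects with a follow-up DSA or known re-treatment, with that denominator. State how many used a substitute and how many had no follow-up angiogram, including deaths. Add missing-as-failure and missing-as-success bounds. The bounds also matter because known re-treatments enter as failures while other unimaged subjects are left out, so the main rate can lean low.

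For mRS, state in the same three places that the substitute is the last available post-procedure score, with death as 6, and never the pre-procedure score.

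The cost is wording in three places and one extra table, with no new data collection. The reported six-month rate may be less favourable, and its interval will be wider.
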